The present study includes a documented plan for the collection, storage, protection and analysis of research data. The key components of this plan include restriction from unauthorized access to identifiable subject data, storage of data to protect against inadvertent loss, and use of appropriate database software tools to maintain integrity of data for subsequent analyses. All research files will be coded using a study identification number. Subject identifying information and PHI will be stored separately from other data collected for this study and will only be accessible by those investigators, Lifespan or University clinicians, or staff who have a need to know this information for the purpose of conducting the study. All identifying data will be stored in locked cabinets and locked offices or in password-encrypted files. Access to these files is limited to investigators and support personnel with the need to enter or analyze data.

All research and clinical information obtained is kept confidential unless the subject is an immediate danger to him or herself or to others (Note: clinically relevant but not life threatening information may be shared with outside personnel with subject permission). During crisis situations, this clinical information may be provided to other clinicians (or family members) in order to facilitate appropriate treatment and minimize the risks of self-harm or harm to others. This information may include the subject's clinical diagnosis, psychiatric and medical history, current medication and treatment status, response to psychiatric or substance abuse treatment, financial and social resources, and history of suicidal behavior, if known.

If study personnel identify inappropriate treatment practices by an outside professional (e.g., inappropriate/dangerous medication combinations given to a vulnerable elder) key study personnel will be consulted and a course of action will be planned that balances subject confidentiality with his or her safety. Normally, consent will be obtained from the subject to speak to the other treating professional and express concerns. If the subject refuses to provide consent to speak with the professional, the degree of danger to the subject will be the primary barometer to determine the appropriate steps.

6. Certification of Research Personnel in the Protection of Human Subjects

In order to ensure appropriate human research knowledge, all study personnel interacting with subjects or with access to subject research will have completed mandatory training in the protection of human research participants per guidelines issued by the U. S. Department of Health and Human Services, Office for Human Research Protections (see <http://ohrp.osophs.dhhs.gov/>) and per guidelines of the University of Rochester Medical Center. Any additional personnel will complete this training before interacting with study subjects.

Consistent with University of Rochester Research Subjects Review Board (RSRB) policy, all investigators and research staff will complete certification by the RSRB—required completion of a course that contains seven modules dealing with topics such as “Ethics and Federal Regulations,” “Roles and Responsibilities of the Investigator and the Study process,” and “Roles and Responsibilities of Institutions in Human Subjects Research,” among others. The program provides a substantial resource to the investigator for understanding the ethics and regulations governing research with human subjects.

It is also University of Rochester policy that all research and clinical staff who may be in contact with protected health information (PHI) demonstrate a working understanding of the University of Rochester's Notification of Health Policies and Practices form. This information form describes to patients and research subjects the University's policies and procedures regarding PHI, consistent with the federal Health Insurance Portability and Accountability Act (HIPAA) and with other relevant university regulations and local, state, and national legislation. All investigators and research staff will complete an information and training session on HIPAA legislation, the University's Notification of Privacy Practices, and on ethical conduct of research in accordance with this legislation and with University regulations. This training session will be developed, in tandem, by training staff in the Department of Psychiatry and by the HIPAA compliance officer for Lifespan.

7. Potential Benefits to the Subjects

Half of the study subjects will receive a volunteering intervention aimed to reduce loneliness – an intervention that targets a significant risk factor for reduced well-being, morbidity and mortality. The other half of subjects will receive an evidence based life review intervention that has demonstrated benefits for well-being. Thus, the potential benefit to the individual may be significant. Subjects may additionally benefit from participating in research interviews and completing the questionnaire measures, as these assessments provide them with

the opportunity to be carefully listened to and comprehensively evaluated. They may further benefit from feelings of altruism connected with participation in research designed to better understand the mental health needs and experiences of community-residing older adults. Given the minimal risks associated with the proposed research and the substantial gains both to the individual and older adults more broadly, benefits appear to outweigh the risks.

8. Importance of the Knowledge to be Gained

There is a pressing public health need to find interventions that reduce loneliness in later life. *Reducing loneliness would significantly improve the lives of older adults by improving well-being and promoting health and longevity.* There is infrastructure nationwide that provides volunteering opportunities and support for older adults—the Senior Corps—indicating that volunteering is an accessible intervention for older adults. If shown effective at reducing loneliness, dissemination efforts would involve connecting primary care patients and aging services clients who are lonely with this type of intervention, which we have shown to be feasible in our companion study of older adult peer companionship, The Senior Connection (TSC).

9. Alternatives to Participation

Regarding alternative interventions, subjects will not be prohibited from seeking out supportive social services, or volunteering their services to others (for ethical reasons), but subjects will be asked to refrain from initiating new long-term volunteering experiences during their time in the study. If a subject in the volunteering group does engage these services, he/she will be followed for the full 12 months, with documentation of the nature and extent of that engagement, and evaluation of its impact on the outcomes of interest.

10. ClinicalTrials.gov Requirements

In line with NIH requirements, we plan to register the trial.

VII. SUBJECT IDENTIFICATION, RECRUITMENT AND CONSENT/ASSENT

1. Method of Subject Identification And Recruitment

Recruitment strategies involve:

- 1) initial contact:
 - a. informational letter sent to home
 - b. flyers and advertisements
 - c. HARP database study (RSRB 67245) referrals
 - d. In-person recruitment in PCP offices
 - e. Direct referral via providing an informational letter from physicians and care managers
 - f. Informational Sessions
- 2) informational phone call;
- 3) in-person interview for written informed consent and assessment.

As described in the Procedures section, recruitment via informational letter will involve completing a data request (via secure software, and only involving patients within the covered entity), and cleaning the data on a secure, password-protected device. A designee from the practice will then be given an opportunity to review the list and exclude individuals as needed. After the list of patients has been “cleared,” staff from the research team, the Center for Research Support or The University Copy Center will prepare and send informational letters to each individual. The letters will briefly explain the study, as well as inform potential subjects that their participation is entirely voluntary, and that their decision regarding participation in this study will in no way affect their medical care. Additionally, the letter will invite those who may be interested to call research staff.

The phone call will involve providing potential subjects with additional details about the study. For those who are willing to continue, the research coordinator will schedule an in-person assessment within five business days. During the assessment, the study coordinator will again explain the study and obtain written consent for the subject to participate. Baseline assessments will be completed. Finally research staff will remind the subject of the randomization process and the assessment follow-up schedule and answer any remaining questions. If eligibility can be confirmed by study coordinator at the baseline

interview, the study coordinator will randomize the subject at that time. If there are any eligibility concerns, the study coordinator will notify the subject that randomization will happen at a later time. After the interview, study staff will review the assessment with the PI. Once determined to be suitable for randomization, staff will randomize the subject and call him/her to notify the subject of the group to which he/she has been assigned.

2. Process of Consent

The CRC will obtain written consent from subjects before the baseline in-person assessment only after subjects have received both verbal and written explanations of the study and indicated their full understanding. They will be informed that the study is designed to examine the social supports of older adults in the community, and whether people receive benefit from participating in social types of volunteering. They will be informed of their rights as research subjects, including the right to refuse to participate in the study, and to withdraw their consent at any time, as well as potential risks and benefits of participation, including financial compensation, and rights to privacy and confidentiality. Data storage and safety will also be described to them. Finally, the process of randomization to one of two conditions will be described; subjects will be told that if they choose to participate they will randomly assigned to one of two conditions: volunteering or life review.

3. Subject Comprehension and Capacity to Consent

A Capacity for Informed Consent protocol will be implemented for all potential participants (see attached document: "Determination of Capacity for Informed Consent"). The capacity assessment will consist of a series of open ended questions administered to the subject that follow explanation of the study. It will address the subject's knowledge and understanding of the study's objectives, the voluntary nature of participation, ability to withdraw at any time, consequences of withdrawing, possible risks and benefits of participation. For subjects who have difficulty in one or more of these areas, further review of the relevant elements of the study will be provided in order to improve their knowledge and understanding to a level that enables them to make a meaningful choice about participation. A form (i.e., "Determination of Capacity for Informed Consent") will be completed for each subject documenting the results of the decision-making capacity determination, a copy of which is maintained with the consent form.

4. Debriefing Procedures

At the final 12 month interview, research staff will give those assigned to life review information about volunteering. If they are interested, a Lifespan brochure that lists all Lifespan programs and contact information will be given to the subject.

5. Consent Forms

See attached.

6. Documentation of Consent

All signed consent forms will be stored in a locked file in a locked office, separate from other non-identifying subject data. Only study staff will have access to these files. All subjects will receive a signed copy of the consent form for their records.

7. Costs to the Subject

There are no costs to the subject. Parking at URMC will be paid for by the study. For those who take the bus, a bus pass will be provided.

8. Payment for Participation

Participants will be paid \$50 for the baseline interview, \$10 for each internet-based/mailed/in-person survey follow-ups (3 and 9 months), and \$35 for in-person interviews at 6 and 12-months. Each participant, therefore, may be reimbursed a maximum of \$140 for their time and effort.

References

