c) Inclusion Criteria: age \geq 60 yrs; English speaking; endorse clinically significant loneliness, as measured by a score of 6 or greater on the 3-item UCLA Loneliness Scale during an initial phone screen; a score of 2 errors or fewer on the 6-item screener (a brief cognitive functioning scale) in the initial phone screen; ability to supply their own transportation (or have alternate transportation services, including the city bus or services such as Lifeline), which are Senior Corps and Lifespan requirements for participation. Subjects will have sufficient cognitive functioning to provide informed consent and to understand the study requirements and procedures (additional details below).

d) Exclusion Criteria: presentation at screening and the baseline interview with any of the following: currently volunteering through Lifespan's Retired & Senior Volunteer Program (RSVP), current problem drinking, psychosis, significant cognitive impairment (MOCA<22), illiteracy, felony conviction (via self-

report, as this a requirement of Lifespan, which runs the volunteering intervention), and hearing or other problems that preclude engagement as a volunteer.

Other inclusion/exclusion considerations are as follows: 1) We will restrict subjects to those who can speak *English* because the agency that offers the volunteer program (Lifespan) cannot accommodate non-English speaking volunteers at this time due to training and supervision needs; 2) given that our active control condition involves reading and writing, illiteracy is an exclusion criterion; 3) subjects will **not** be required to cease on-going *volunteer activities* (for ethical reasons). Subjects will be asked to refrain from initiating *new* long-term volunteer activities during their 12 months of involvement with the study (one-time only activities are allowed as these are unlikely to foster social connections). We believe this constraint is ethically sound because subjects are permitted to continue current volunteer roles and combined with the fact that abstaining from new volunteering will not expose subjects to risk. Further, subjects assigned to control will be told they will be connected with our community's Senior Corps program at the end of their study involvement if they choose. Throughout the study, we will assess for "dose" of both study and out-of-study volunteer and informal caregiving activities, and covary for this factor in the unlikely event that differences emerge across conditions.

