Attitudes to Ageing Questionnaire AAQ	Feelings on getting older	This set of self-report questions allow subjects to express their attitudes towards aging.	5 minutes In-person interviews

Total estimated time for entire baseline interview		90 – 153 minutes
--	--	------------------

f) Study Conditions:

Volunteering condition: HOPE volunteers are supported by Lifespan and the Senior Corps. The Senior Corps is one of Lifespan's many programs for seniors in the community. Its objective is to match seniors with volunteer opportunities that match their interests and capabilities. Subjects will begin training at Lifespan within two weeks of randomization. Aging Services agency-supported volunteer placement in a social volunteer activity is initiated for one year. The target expectation for volunteering is 4 times per month (about once per week). Lifespan collects monthly timesheets, which will include the number of hours and types of volunteer

activities done. The Senior Corps provides a small reimbursement for travel to volunteers as needed for travel related to volunteering. The other component of the intervention is on-going training (“booster sessions”), volunteer support groups, and educational activities offered by Lifespan. These gatherings for volunteers serve to promote retention in the program, assist volunteers with any problems/issues that have arisen, and promote social connectedness among volunteers. This is standard Lifespan policy.

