
g) Analytic Procedures:

Power analysis is conducted to test treatment effects by the intent-to-treat (ITT) analysis for the primary hypothesis. We assume a conservative 20% attrition rate and a 0.3 within-subject correlation. A sample size of N = 300 (or N = 150 per treatment group) will allow us to detect a small effect size of 0.2 for loneliness, with 80% power based on a two-sided type I alpha = 0.05. The assumed within-subject correlation of 0.3 reflects the relatively long time lag between consecutive assessments. The proposed sample size also has 80% power to detect 32% mediation effects for loneliness, a continuous outcome. If full mediation is not achieved for any of the mediators considered, 32% mediation effects are sufficiently large to be of clinical importance for the outcomes of interest.

Descriptive statistics will be computed to summarize distributions of each outcome, with means and standard deviations for continuous outcomes and percent for categorical outcomes. Two-sample t tests (or the Mann-Whitney-Wilcoxon rank sum test) and Chi-squares will be used to examine balance of treatment randomization for continuous (if distributions are highlight skewed) and categorical variables. The primary hypotheses are concerned about the effectiveness of volunteering on reducing loneliness vs. control. Examination of mechanisms (mediation, Aim 2) as well as dose-response relationships (Aim 3) and moderators (Aim 3) of the intervention will also be examined. Aim 1 (and Aim 3 H4 on moderation) will be tested using longitudinal regression models, while the mediation hypothesis (Aim 2) will be examined by structural equation models, and dose-response relationships (Aim 3) by structural mean models.

The two most popular longitudinal models are the generalized linear mixed-effect models (GLMM) and the weighted generalized estimating equations (WGEE). Weighting is based on inverse probability of drop-out, extending standard GEE from valid inference only under missing completely at random to missing at random, similar to GLMMs. For inference about treatment effects, both models can be applied. However, parametric

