The ITT analysis for Aim 1 provides intervention effects averaged over all subjects randomized to the intervention conditions. When intervention compliance (volunteering hours/satisfaction for subjects in the volunteering condition) demonstrates a dose-response relationship, as we hypothesize in Aim 3, complier average causal effects (CACE) are appropriate; thus we will use them to test Hypothesis 3. CACE is a compliment to ITT analyses and provides an answer to a different question than is answered by ITT analyses (i.e., the result of complying vs. being offered an intervention).⁷¹ CACE provides valid causal inference because it maintains randomization and includes all subjects in the analysis, as with ITT.⁷² CACE provides different intervention effects for individuals depending on their levels of compliance, which can be quite informative, especially when there is large variability in intervention compliance and strong dose-response relationships. The ITT and CACE estimates from a similar intervention study by Gruenewald, et al.⁷³ show that not only were the CACE effect sizes much larger than their ITT counterparts (small ITT vs. large CACE effect size), but the temporal trend also reversed; while the ITT effect sizes decreased, the CACE effect sizes increased from 4 months to 12 months post intervention, indicating substantial heterogeneity in intervention compliance and strong dose-response relationships. Since volunteering time is only required for the volunteering condition, standard statistical models cannot be used to perform CACE analysis. The CACE approach enables an estimate of the treatment effect at each level of "compliance" (i.e., amount of hours volunteered), without the need for a measure of compliance in the control group. In this way, we will be able to tell how well volunteering reduces loneliness at different "doses" of volunteering. The two most popular methods for addressing intervention compliance are the parametric principal stratification (PS) and the semi-parametric structural mean model (SMM).⁷⁴⁻⁷⁶ Unlike the PS, the SMM not only allows for continuous dose variables, but also requires no parametric model for data distribution such as normality, thereby yielding robust inference for a broader class of data distributions. We will use the latest SMM based on the structural functional response models (SFRM) for our CACE analysis, which not only allow for continuous, but also multiple dose variables.⁷⁴⁻⁷⁶ We are particularly interested in potential non-linear dose-response relationships so that we may determine optimal dose intervention whereby increased exposure (i.e., number of hours volunteered) becomes less worthwhile (in terms of reducing loneliness).

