
Aim 1 compares subjects randomized to either the volunteering or control on loneliness (continuous variable). **H1a:** There will be a condition effect on loneliness at all time points indicating differing levels of loneliness in the direction: control > volunteering. Longitudinal models will be employed with loneliness as the response, and condition, time and their interaction as the predictors, controlling for age, gender. If a significant difference exists (a significant time by condition interaction), appropriate linear contrasts will confirm the hypothesized directional effects. For **H1b**, the same analytic strategy will be used, but with quality of life (continuous) as the response variable. Aim 2 involves mediation analysis: is to examine perceived usefulness and social support as mediators of the intervention effect on loneliness. **H2a:** Increases in social engagement at 6 months is hypothesized to mediate the effect of intervention condition on decreased loneliness at 12 months. The SEM-based mediation models will be applied, with social engagement as the mediator, intervention condition as the predictor and loneliness as the outcome, controlling for age, gender. If the null of full mediation is rejected, we will estimate direct, indirect and total effects to assess the strength of mediation. The same analytic strategy

will be used for perceived usefulness and social support (**H2bc**). **Aim 3** involves when volunteering will provide maximal benefit. **H3:** Greater hours (compliance) and satisfaction will be associated with better outcomes. We will apply the SFRM-based SMM to analyze dose-response relationships. We will first model dose using non-parametric methods and then characterize the patterns using parametric methods. This allows us to capture detailed dose and response relationships and provide more interpretable findings. **H4:** The longitudinal model for H1a will be used with functional status as a moderator variable.

h) Data and Safety Monitoring Plan:

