- b. The interventions, volunteering and life review, carry the risk of causing emotional distress or fatigue. Our volunteers may experience stressors as a result of volunteering.. Our intervention includes support for volunteers through these experiences. Subjects assigned to life review may write and think about memories of negative experiences; they will receive support for such experiences. No sustained negative effects are expected, but negative outcomes from behavioral interventions cannot be ruled out. The volunteer coordinator and care manager are experienced in working with older adults and in assisting volunteers through situations involving loss. The life review supervisor is also experienced in working with older adults and assisting participants through the experiences of recalling stressful memories.
- c. Regarding alternative interventions, subjects will not be prohibited from seeking out supportive social services, or volunteering their services to others (for ethical reasons), but subjects will be asked to refrain from initiating *new* long-term volunteering experiences during their time in the study. If a subject in the volunteering group does engage these services, he/she will be followed for the full 12 months, with documentation of the nature and extent of that engagement, and evaluation of its impact on the outcomes of interest.

3. Protection Against Risks

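### The rule to covary for volunteering dose includes the study intervention itself and conflicts with the intention-to-treat model for Aim 1

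*Combined protocol and SAP*

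**What the plan says.** Section II.d (Exclusion Criteria), in the third of its further eligibility considerations, lets participants keep existing volunteer roles and asks them not to start new long-term ones. It then says that during follow-up the team will assess the dose of "both study and out-of-study volunteer and informal caregiving activities, and covary for this factor in the unlikely event that differences emerge across conditions". No outcome, aim or model is named.

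Section III.g (Analytic Procedures) sets out the primary analysis. On sample size: "Power analysis is conducted to test treatment effects by the intent-to-treat (ITT) analysis for the primary hypothesis". On the estimand: "The ITT analysis for Aim 1 provides intervention effects averaged over all subjects randomized to the intervention conditions". On the H1a model: "Longitudinal models will be employed with loneliness as the response, and condition, time and their interaction as the predictors, controlling for age, gender". H1b uses the same strategy for quality of life. No dose term appears.

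Study dose has its own place. Section III.f sets a target of 4 volunteering occasions a month in the volunteering arm. Section III.g assigns dose-response (H3) to a structural mean model, giving as the reason: "Since volunteering time is only required for the volunteering condition", standard models cannot be used for that analysis.

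For participants in the volunteering group who take up outside services or volunteering, Sections IV.2.c and IV.9 promise follow-up "with documentation of the nature and extent of that engagement, and evaluation of its impact on the outcomes of interest".

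**The concern.** The Section II.d rule has two defects as written.

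First, its trigger is treated as improbable, yet for study volunteering it is the design of the trial. Current RSVP volunteers are excluded, the control arm is offered a Senior Corps connection only after its participation ends, and the volunteering arm is placed in the program.

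Second, dose is measured after randomization and, under H3a, is expected to carry part of the effect. Conditioning on it in the treatment comparison removes that part, inflates the standard error because dose and arm are strongly correlated, and opens the comparison to confounding by whatever makes some people volunteer more.

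Two sections therefore give different covariate sets for what may be the same primary analysis, and the choice between them could be made after the data are seen.

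**Working it through.** **Baseline for comparison.** Section III.g gives 150 per arm, 20% attrition, within-subject correlation 0.3, effect 0.2 SD, two-sided alpha 0.05 and 80% power. Taking the mean of four follow-ups:
- Variance = (1 + 3 × 0.3)/4 = 0.475. With 150 × 0.8 = 120 per arm, SE = √(2 × 0.475/120) = 0.089.
- Power = Φ(0.20/0.089 − 1.96) ≈ 0.61; simulation gave about 60%.

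This does not reproduce the stated 80%. Of the two-sided variants tried, only a baseline-adjusted mean (variance 0.475 − 0.09 = 0.385) with attrition ignored comes close, at 79.7%. The documents do not give the power formula, so this is a side observation. The 60% is a reference for what follows, not the plan's figure.

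**Is the trigger met?** With control study dose 0 and a volunteering mean of 4 a month (assumed SD 2 to 4), z = 4/√(SD²/120), or about 22 to 11. In simulation with the hours model below, arms differed at p < 0.05 in all 2000 replicates, even with 80% non-starters.

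**Study hours as covariate.** Assumed hours among starters: mean 8 a month, SD 5, with 15% non-starters; controls 0.
- Mean in the volunteering arm = 0.85 × 8 = 6.8. Variance = 0.85 × (8² + 5²) − 6.8² = 29.41. Averaged over both arms, within-arm variance = 29.41/2 = 14.705.
- Between-arm variance = 6.8²/4 = 11.56, so arm–hours r² = 11.56/(11.56 + 14.705) = 0.44.
- SE = 0.089 × √(1/(1 − 0.44)) = 0.119.
- Let a share s of the effect run through hours: reduction = 0.20 × [(1 − s) × arm + s × hours/6.8]. The arm coefficient given hours is 0.20 × (1 − s).

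**One combined study-plus-outside total.** Assumed outside hours: mean 4, SD 4, in both arms.
- Within-arm variance of the total = 14.705 + 16 = 30.705.
- Pooled slope = s × (0.20/6.8) × 14.705/30.705 = 0.0141 × s.
- Adjusted reduction = 0.20 − 0.0141 × 6.8 × s = 0.20 − 0.096 × s.

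| Share through hours | Study hours covaried: reduction (rejection) | Combined total covaried: reduction (rejection) |
|---|---|---|
| 100% | 0.00 (5%) | 0.10 (17%) |
| 50% | 0.10 (14%) | 0.15 (30%) |
| 0% | 0.20 (38%) | 0.20 (48%) |

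Rejection rates are from 6000 simulated trials. Four other hour distributions (mean, SD, non-starters: 8, 5, 30%; 8, 3, 10%; 12, 8, 20%; 4, 3, 15%) gave the same reductions for study hours, with rejection 4–5%, 10–14% and 25–46%. For the combined total, outside SD of 3 to 6 moves the 100% case between 0.08 and 0.14.

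**Hours related to prognosis.** Half the effect through hours, correlation ±0.2 between hours and the outcome residual.
- Covariance = 0.2 × √0.475 × √29.41 = 0.747.
- Spurious slope = (0.747/2)/14.705 = 0.0254; times 6.8 = 0.17.
- At −0.2 (less lonely people volunteer more), the estimate is 0.10 − 0.17 = −0.07, an apparent increase in loneliness.
- At +0.2 the reduction is 0.27.

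Building the correlation differently gave an increase of 0.03 and a reduction of 0.23. A separate setting with unit outcome SD, a dose of mean 4 and SD 2, and correlation 0.3 gave reductions of about 0.6 to 0.8. The direction of bias is clear in each case; its size depends on the assumptions.

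**The case against.** The strongest reply is that only outside activity was meant. The sentence closes a paragraph about existing and new outside volunteering, and calling a difference unlikely makes sense only for activity that could be similar in both arms. Authors who explain in Section III.g why ordinary models cannot handle volunteering time would hardly plan to enter it in one. A specific model in the analysis section could also be taken to override a remark under eligibility. On that reading there is no computed size for the bias.

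The calculations are simplified too. They use ordinary least squares on visit averages among completers, whereas the plan uses GLMM and weighted GEE with a condition-by-time interaction.

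Much of this stands. The narrower intent is plausible, and the figures show that the estimand can change, not by how much it would in this trial. It does not settle the matter. The text names study and outside activity together, and neither Section III.g nor the 2022 addendum limits the rule or gives one section precedence. The narrower reading also leaves a covariate that is measured after randomization, possibly affected by assignment, included only if the data show a difference, and absent from the H1a model.

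**Conclusion.** The concern holds and should be corrected before outcomes are compared by arm. The conflict is established from the text alone: Section II.d includes study dose in a covariate rule whose condition the design guarantees, and Section III.g specifies an intention-to-treat model without it.

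The harm is conditional on the rule being applied to Aim 1. In that case the condition coefficient stops being the intention-to-treat effect. Under the assumed hours its standard error rises from 0.089 to about 0.12. Without confounding, the estimated reduction falls from 0.20 to anywhere between 0.20 and 0.00 according to the share acting through hours, with 0.00 as the extreme. With modest confounding it can be biased in either direction. The documents supply only the target of 4 times a month; the hours, shares and correlations are assumed. If only outside activity was meant, the problem is smaller and the documents give no basis for sizing it.

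**What to change.** Replace the Section II.d sentence with one stating that study volunteering, outside volunteering and caregiving will be recorded and that none of these doses enters the Aim 1 models for H1a or H1b, which stay as given in Section III.g. Study dose is analysed only in the Aim 3 structural mean model. Outside volunteering and caregiving are reported by arm, and any adjustment for them is a labelled sensitivity analysis. That retains the evaluation of outside engagement promised in Sections IV.2.c and IV.9.

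The cost is one sentence of protocol text. No new data or new model is needed, because the primary model without dose and the dose-response method are both already in the plan.
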